## **6.7. Smartphone**

Subjects will use their own Smartphone during this study.

## **6.8. Anticipated Devices Change**

Device change(s) may occur during the study. Therefore, a protocol amendment will be submitted in the event the device change(s) are made.

## **6.9. Product Accountability**

Good clinical research practice requires that investigators and research teams ensure accurate accountability for any investigational device used in a research trial. It is expected that all investigational devices will be used in the manner intended during the study, that they will be stored under appropriately controlled conditions, and that they will be used only by (on) subjects who have consented to participate in the research study.

Any investigational device being used in clinical research must be strictly accounted for and will not be shipped to any site unless all of the necessary approvals (e.g. Regulatory, Institutional Review Board [IRB]) have been received. This includes keeping records of:

1. Center receipt and inventory management
2. Storage
3. Subject Disbursement
4. Return (by Subjects and Center) and/or disposal

During the conduct of the study the investigational center staff will account for and document the following:

**Table 5 Device Accountability Requirements**

Device	Record on Site Received eCRF	Record Disbursement, Returned or Not Returned from Subject on Device Identification eCRF	Subject Return Device to Investigational Center	Record Returned or Not Returned to Sponsor on Site Returned eCRF	Site Return Device to Sponsor at Conclusion of Study
MiniMed™ 670G Insulin Pump, version 4.0 Tel-D (MMT-1740)	Yes	Yes	Yes	Yes	Yes
Guardian™ Link (3) Transmitter	Yes	No	Yes	Yes	Yes (used and unused)
Guardian™ Sensor (3) (MMT-7020)	Yes	No	No	Yes	Dispose or return unused to sponsor
CONTOUR® NEXT LINK 2.4 Study Meter (MMT-1352)	Yes	Yes	Yes	Yes	Dispose or return unused to sponsor

The investigational center will promptly notify the sponsor of any device handling violation that might impact either the safety or welfare of subjects or data integrity.

#### **6.9.1. Receipt and Inventory of Investigational Devices by Investigational Center**

- Upon receipt of the study devices, investigational center staff take inventory of the shipment, making sure that information on the packing slips/invoices matches exactly the contents of the containers, as applicable, including:
  - Ship to Address
  - Reference Number
  - Device Type
  - Quantity

- Quantity per package
- Lot number (where applicable)
- Serial number (where applicable)
- Ensure that devices and supplies received have not reached or exceeded their expiration date
- Sign and date the packing slips/invoices, noting any discrepancies, and file in appropriate study binder
- Notify the study monitor of any discrepancies
- Enter the study device information on the appropriate eCRF in the study database.

#### **6.9.2. Storage of Study Devices at Investigational Center**

Study devices are to be stored in a secure environment with access limited to authorized research personnel. Study devices are stored in the proper environmental conditions as identified in the IFU/labeling.

#### **6.9.3. Disbursement of Study Devices**

Each time a study device is disbursed to a subject by the investigator or authorized member of the research team, all required eCRF and source documentation will be completed. Documentation may include:

- Date of disbursement
- Subject ID
- Lot number(s)
- Serial Number
- Reference Number
- Amount dispensed

#### **6.9.4. Return or Disposal of Study Devices**

After use by the subject, the investigational center is expected to accept and retain all devices as described in Table 5 and store them in a secure environment. If containers/units/devices are missing, the reasons should be documented in the applicable eCRF. If discrepancies between the amounts used by subjects and the amounts expected to be returned exist, the reasons should be documented in the applicable eCRF.

Requirements for return of devices by subjects to the investigational center and return of device by the investigational center to the sponsor are listed in Table 5. The devices that are being returned to the investigational center may be returned to the sponsor as subjects complete the study, at the EOS visit or upon sponsor request.

Other unused consumable devices (i.e., infusion sets, alcohol wipes, study meter supplies, tape, etc.), supplies or materials may be returned to the sponsor, they may be retained by investigational centers for

educational purposes only, or they may be disposed of properly by investigational center staff. Any used commercial study meter may be kept by subjects.

Disposable devices and supplies that have been *used* by a subject will be disposed of properly by the subject or the investigational center staff during the conduct of the study.

All study devices that are required to be entered into the study database must be accounted for as described above before they are returned to the sponsor.

## 7. Selection of Subjects

### 7.1. Study Population

A total of up to 200 subjects will be enrolled at up to 15 investigational centers across the US in order to have up to 150 subjects who complete the study.

It is expected that at least N=12-18 subjects will participate in each phase during Feasibility 2.

### 7.2. Subject Enrollment

Subjects will be considered enrolled in the study upon signing the Informed Consent Form (ICF)/Assent form.

A subject will be assigned a unique study subject ID (SID) via the eCRF, which is a 9-digit code (326XXXXXX). The first three numbers refer to the CIP number (326), the next three numbers refer to the investigational center number, and the last 3 numbers refer to the subject number assigned during Visit 1 (e.g., 326002001 is subject 001 from site 002).

The investigator will maintain a log of all subjects enrolled in the clinical study, assigning a SID linked to their names, alternative SID, and contact information.

### 7.3. Inclusion Criteria

#### *General Inclusion Criteria*

1. Subject is age 2-80 years at time of Visit 1.  
**Note:** See staged enrollment reference for adult and pediatric subjects in the Study Design section
2. Subject has a clinical diagnosis of type 1 diabetes.
  - a. Subjects 7 years of age and older: Diagnosed at least 1 year prior to Visit 1
  - b. Subjects 2-6 years of age: Diagnosed at least 3 months prior to Visit 1

#### *Study-specific inclusion criteria*

3. Subject must have a minimum daily insulin requirement (Total Daily Dose) of greater than or equal to 8 units.

4. If subject has a history of hypothyroidism, must have at least 1 documented normal thyroid-stimulating hormone (TSH) on historical labs within 12 months of Visit 1. A subject without a history of hyperthyroidism is not expected to have a TSH test.
5. Subjects and their parent(s)/guardian(s) must have Internet access , a computer system that meets the requirements for uploading the study pump and Smartphone that meets study requirements.
6. Subject must have a companion or caregiver available at night for the duration of the study period who resides (or will live) in the same building (or home). This requirement may be verified by subject report at screening visit.
7. If subject has celiac disease, it has been adequately treated as determined by the investigator.
8. Subjects and their parent(s)/guardian(s) are willing to take one of the following insulins and can financially support the use of either of the 2 insulin preparations throughout the course of the study (i.e. co-payments for insulin with insurance or able to pay full amount)
  - a. Humalog™\* (insulin lispro injection)
  - b. NovoLog™\* (insulin aspart)

## 7.4. Exclusion Criteria

1. Subject has a history of 1 or more episodes of severe hypoglycemia, which resulted in any the following during the last 1 year prior to Visit 1
  - a. Medical assistance (i.e. Paramedics, Emergency Room (ER) or Hospitalization)
  - b. Coma
  - c. Seizures
2. Subject is unable to tolerate tape adhesive in the area of sensor placement.
3. Subject has any unresolved adverse skin condition in the area of sensor placement (e.g., psoriasis, dermatitis herpetiformis, rash, Staphylococcus infection).
4. Women of child-bearing potential who have a positive pregnancy test at Visit 1 or plan to become pregnant during the course of the study
5. Females who are sexually active and able to conceive will be excluded if they are not using an effective method of contraception and do not agree to continue using an effective method of contraception for the duration of the study as determined by investigator.
6. Subject has a cardiovascular condition which the Study Investigator determines should exclude the subject, e.g. ventricular rhythm disturbance, hypertrophic cardiomyopathy, recent myocardial infarction in the last year prior to Visit 1.
7. Subject is being treated for hyperthyroidism at time of Visit 1.
8. Subject has a diagnosis of adrenal insufficiency.
9. Subject has had Diabetic Ketoacidosis (DKA) within 1 year prior to Visit 1.
10. Subject has taken any oral, injectable, or intravenous (IV) glucocorticoids within 8 weeks from time of visit 1, or plans to take any oral, injectable, or IV glucocorticoids during the course of the study.
11. Subject is actively participating in an investigational study (e.g., drug or device) wherein he/she has received treatment from an investigational study (drug or device) in the last 2 weeks prior to Visit 1. Please note participation in observational study is acceptable.
12. Subject has been hospitalized or has visited the ER in the 6 months prior to Visit 1 resulting in a **primary diagnosis** of uncontrolled diabetes.
13. Subject is currently abusing illicit drugs.
14. Subject is currently abusing alcohol.
15. Subject is using pramlintide (Symlin), DPP-4 inhibitor, liraglutide (Victoza or other GLP-1 agonists), metformin, canagliflozin (Invokana or other SGLT2 inhibitors) at time of Visit 1.

16. Subject has a history of visual impairment which would not allow subject to participate in the study and perform all study procedures safely, as determined by the investigator.
17. Subject has elective surgery planned that requires general anesthesia during the course of the study.
18. Subject diagnosed with current eating disorder such as anorexia or bulimia.
19. Subject has been diagnosed with chronic kidney disease that results in chronic anemia.
20. Subject is on dialysis.
21. Subject has serum creatinine of >2 mg/dL, as confirmed through historical labs within 1 year prior to Visit 1.
22. Subject is a member the research staff involved with the study.

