	
3. Subject has any unresolved adverse skin condition in the area of sensor placement (e.g., psoriasis, dermatitis herpetiformis, rash, Staphylococcus infection).
 
4. Women of child-bearing potential who have a positive pregnancy test at Visit 1 or plan to become pregnant during the course of the study
 
5. Females who are sexually active and able to conceive will be excluded if they are not using an effective method of contraception and do not agree to continue using an effective method of contraception for the duration of the study as determined by investigator.
 
6. Subject has a cardiovascular condition which the Study Investigator determines should exclude the subject, e.g. ventricular rhythm disturbance, hypertrophic cardiomyopathy, recent myocardial infarction in the last year prior to Visit 1.
 
7. Subject is being treated for hyperthyroidism at time of Visit 1.
 
8. Subject has a diagnosis of adrenal insufficiency.
 
9. Subject has had Diabetic Ketoacidosis (DKA) within 1 year prior to Visit 1.
 
10. Subject has taken any oral, injectable, or intravenous (IV) glucocorticoids within 8 weeks from time of visit 1, or plans to take any oral, injectable, or IV glucocorticoids during the course of the study.
 
11. Subject is actively participating in an investigational study (e.g., drug or device) wherein he/she has received treatment from an investigational study (drug or device) in the last 2 weeks prior to Visit 1. Please note participation in observational study is acceptable.
 
12. Subject has been hospitalized or has visited the ER in the 6 months prior to Visit 1 resulting in a primary diagnosis of uncontrolled diabetes.
 
13. Subject is currently abusing illicit drugs.
 
14. Subject is currently abusing alcohol.
 
15. Subject is using pramlintide (Symlin), DPP-4 inhibitor, liraglutide (Victoza or other GLP-1 agonists), metformin, canagliflozin (Invokana or other SGLT2 inhibitors) at time of Visit 1.
 
16. Subject has a history of visual impairment which would not allow subject to participate in the study and perform all study procedures safely, as determined by the investigator.
 
17. Subject has elective surgery planned that requires general anesthesia during the course of the study.
 
18. Subject diagnosed with current eating disorder such as anorexia or bulimia.
 
19. Subject has been diagnosed with chronic kidney disease that results in chronic anemia.
 
20. Subject is on dialysis.
 
21. Subject has serum creatinine of >2 mg/dL, as confirmed through historical labs within 1 year prior to Visit 1.
 
22. Subject is a member the research staff involved with the study.

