## 9.10. Subject Exit, Withdrawal or Discontinuation

Subjects may choose to withdraw from the study at any time by notifying investigational center staff of their intent.

If a subject chooses to end his or her study participation or if the subject is removed from the study at the Investigator's discretion or for failure to meet the study requirements, the reason for withdrawal must be documented. All study devices and supplies must be returned (as applicable) and documented both in source documents and on an eCRF.

Subjects may also be withdrawn from the study at the discretion of the Investigator. A subject will be withdrawn from the study if:

- In the opinion of the investigator, the subject's health or safety would be compromised by continuing in the study
- In the opinion of the investigator, it is in the subject's best interest to discontinue participation in the study
- During the course of the study, subject begins participation in another investigational study (drug or device).
- Subject participates in a phase that requires a Smartphone as part of the study requirements and subject does not have a Smartphone.
- During the course of the study, subject begins abusing illicit drugs.
- During the course of the study, subject begins abusing alcohol.
- During the course of the study, subject begins using pramlintide (Symlin), DPP-4 inhibitors, liraglutide (Victoza or other GLP-1 agonists), metformin, canagliflozin (Invokana or other SGLT2 inhibitors).
- During the course of the study, the subject demonstrates that he/she is not able to comprehend instructions for study procedures, as evaluated by the appropriate research staff.
- During the course of the study, subject is taking oral, injectable, or IV glucocorticoids
- During the study, (female) subject becomes pregnant.
- During the study, the subject experiences one severe hypoglycemic episode
- During the study, the subject experiences one episode of DKA
- During the study, subject has a cardiovascular event or any vascular event such as stroke.

Documentation of the reason(s) leading to subject withdrawal will be kept in the subject's source documentation.

For **Study Exit** visits for reason other than subject lost to follow-up, the following information is required:

- Assess and document any reportable AEs (refer to section 10 Adverse Events)
- For study exit visits occurring in the clinic, perform a CareLink™ upload

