### **14.7. Sample Size Justification**

Given that this study is not statistically powered, no sample size calculation was performed. Up to 200 subjects will be enrolled to demonstrate a feasibility of an outpatient study using the Medtronic insulin pump system.

---

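### Exclusion 5 joins its two contraception conditions with 'and', so read literally it never excludes a current user who will not agree to continue

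*Protocol*

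**What the plan says.** Criterion 5 in Protocol Section 7.4 first names the group it applies to: "Females who are sexually active and able to conceive will be excluded". It then gives the conditions. These women are "excluded if they are not using an effective method of contraception and do not agree to continue using an effective method of contraception", and the sentence ends "for the duration of the study as determined by investigator". The synopsis has the same criterion with the same connective.

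The criterion before it, exclusion 4, covers "Women of child-bearing potential who have a positive pregnancy test at Visit 1 or plan to become pregnant during the course of the study". Exclusion 10 has a similar shape: it bars glucocorticoid use in the 8 weeks before Visit 1, or a plan to use them during the study. No inclusion criterion in Section 7.3 mentions contraception. Section 9.10 lists among its withdrawal grounds "During the study, (female) subject becomes pregnant". It does not list stopping contraception. The SAP does not restate the eligibility criteria.

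**The concern.** An exclusion rule that needs two failures at once is narrower than one triggered by either failure. Here the first condition is about the present (is she using an effective method?) and the second about the future (will she keep using one?). A rule meant to secure contraception from Visit 1 to the end of participation would be expected to act on the current user who will not go on. As worded, it cannot.

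Two things are at stake: subject protection and uniform application. Section 9.9.3 treats continuing a subject who did not meet all eligibility criteria as a significant deviation that needs immediate sponsor notification. On the literal text, enrolling a current user who declines to continue breaches nothing in criterion 5, so monitoring has no ground to flag it. With up to 15 centers, some may follow the text and others its presumed purpose.

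**Working it through.** The plan states no figure on this point, so the check is one of logic. For a sexually active female able to conceive, let A = not using an effective method and B = does not agree to continue using one.

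- As written: excluded if A and B.
- With 'or': excluded if A or B.

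| Using at Visit 1 | Agrees to continue | A | B | As written | With 'or' |
|---|---|---|---|---|---|
| yes | yes | false | false | not excluded | not excluded |
| yes | no | false | true | **not excluded** | excluded |
| no | yes | true | false | not excluded | excluded |
| no | no | true | true | excluded | excluded |

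The written rule excludes 1 of 4 combinations and the 'or' rule excludes 3 of 4. They differ in 3 − 1 = 2 rows, and those two rows do not have the same standing.

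*Second row (using, will not continue).* A is false for every current user, so A and B is false whatever she says about continuing. The commitment for the duration of the study therefore never acts on the only women who have a method to continue.

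*Third row (not using, agrees).* The wording is awkward here, because one cannot continue a method not in use. If that is taken to mean that a non-user can never satisfy the agreement, the rule reduces to excluding non-users and the second condition does no work at all. On that reading the current user who declines is still not excluded, so the gap in the second row does not depend on how the third is read.

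*Can the grammar rescue the text?* If a single 'not' governed both verbs, the sentence could mean that a woman is excluded unless she both uses and agrees to continue. The criterion repeats the negative in its second half, so that reading is not available.

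*Comparison with neighbouring criteria.* Exclusion 4 (pregnant now, or planning pregnancy) and exclusion 10 (recent glucocorticoids, or a plan to take them) each pair a present with a future condition and join them with 'or'. Criterion 5 pairs them in the same way and uses 'and'. That points to a drafting slip rather than a chosen policy.

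**The case against.** The strongest case on the other side is that this is a small ambiguity that other provisions and common sense largely cover.

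- **Investigator judgement.** The criterion ends with a determination by the investigator, and many will apply it as if either condition excludes. That is plausible, but the phrase does not change the connective, and eligibility should not depend on a site reading past the text.
- **Other provisions.** A reader might infer that nothing else guards against pregnancy during the study. The documents do not support that. Exclusion 4 removes women who plan a pregnancy, and Section 9.10 lets the investigator withdraw a subject for safety or in her best interest before any pregnancy. Visit details and consent materials sit in separate documents that cannot be checked here. What stands is that none of the provisions available for review is a contraception rule.
- **Two wrongly admitted groups.** A reader might infer from the table that the text wrongly admits two of three at-risk groups. That assumes an intent the protocol does not state. Admitting a woman who is willing to start an effective method is a tenable policy, so only the current user who declines is a clear gap. Nor do combinations count women: the documents give no frequencies, and three of the six phases enrol ages 2-13, where the criterion will seldom apply.
- **Damage to small phases.** A reader might infer that losing a subject to pregnancy would harm phases expected to have at least 12-18 participants. The protocol says "Given that this study is not statistically powered, no sample size calculation was performed", the endpoints are descriptive, and enrolling up to 200 for up to 150 completers already allows (200 − 150)/200 = 25% loss. No estimate or decision rule is shown to change.
- **Risk classification.** Section 10.5 classes the study as significant risk because of the pump, and Table 6 names no pregnancy risk, so the classification adds little to this point.

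**Conclusion.** The point holds for one group. Read literally, criterion 5 does not exclude a sexually active female able to conceive who uses effective contraception at Visit 1 but does not agree to continue it. That runs against the criterion's evident purpose and against the 'or' in exclusions 4 and 10. Not excluded by criterion 5 does not mean eligible, since another criterion may still exclude her. A woman not using contraception who says she agrees also escapes the literal text, but whether she should be excluded is for the sponsor to state.

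The conclusion rests on the literal wording in Section 7.4 and the synopsis and on an inference about purpose from the duration clause and the neighbouring criteria. How many women are affected cannot be estimated from the documents. This is an eligibility drafting error worth correcting. It touches no endpoint, sample size or analysis.

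**What to change.** In Section 7.4 criterion 5 and in the same criterion in the synopsis, replace 'and do not agree' with 'or do not agree', so that either condition excludes. That change would also exclude a woman not using contraception at Visit 1 who is willing to begin. If the sponsor means to admit a woman who starts an effective method at enrollment, the criterion should say so explicitly.

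The cost is one word in two places at the next amendment, plus a short clause if starters are to be admitted, and possibly a few more screen failures. The SAP needs no change.

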## 8. Study Site Requirements

### 8.1. Study Site Activation

During the activation process (prior to subject enrollment), Medtronic will train investigational center staff. If new members join the study investigational center team, they will receive training on the applicable study requirements relevant to their role before contributing to the study.

Prior to performing study related activities, all regulatory requirements shall be fulfilled.

